5.6. Treatment Compliance

The following measures will be employed to ensure treatment compliance:

- All doses will be administered under the supervision of suitably qualified CRU staff.
- Immediately after oral dose administration, a visual inspection of the mouth and hands will be performed for each subject.

- At each dose preparation occasion, a predose and postdose inventory of LOXO-305 will be performed, as appropriate.

5.7. Drug Accountability

The Investigator (or designee) will maintain an accurate record of the receipt of the study supplies (including LOXO-305 tablets and capsules to over-encapsulate LOXO-305) received or procured by Covance. In addition, an accurate drug disposition record will be kept, specifying the amount dispensed to each subject and the date of dispensing. This drug accountability record will be available for inspection at any time. At the completion of the study, the original drug accountability record will be available for review by the Sponsor upon request.

For each batch of unit doses, the empty used unit dose containers will be discarded upon satisfactory completion of the compliance and accountability procedures. Any unused assembled unit doses will be retained until completion of the study.

At the completion of the study, all unused supplies (including all IMP) will be disposed of by the CRU, per the Sponsor's written instructions and/or in accordance with local/state/federal guidelines governing waste disposal of investigational drugs and the CRUs SOPs.

6. CONCOMITANT THERAPIES AND OTHER RESTRICTIONS

6.1. Concomitant Therapies

Paracetamol/acetaminophen (maximum of 2 g/day for up to 3 consecutive days) is an acceptable concomitant medication.

Subjects will refrain from participation in any other investigational study drug trial in which receipt of any investigational drug occurs within 5 half-lives (if known) or 30 days, whichever is longer, prior to dose administration (Day 1).

All prescription/nonprescription medications and over-the-counter medications (including HRT, herbal products, natural or herbal supplements, except for paracetamol/acetaminophen as referenced above) are prohibited for 14 days prior to dose administration (Day 1) and through EOT or ET, unless deemed acceptable by the Investigator (or designee) and Sponsor. This includes, but is not limited to: moderate or strong CYP3A4 and/or CYP3A5 inhibitors or inducers (including herbal products such as St. John's wort), strong P-gp inhibitors, proton pump inhibitors, antacids, H₂-receptor antagonists, and drugs that prolong QT/QTc interval.

Any medication taken by a subject during the course of the study, including details of its dosage, administration, and the reason for its use, will be documented in the eCRF.

The administration of any concomitant medication during the study is prohibited without prior approval of the Investigator (or designee) and Sponsor, unless its use is deemed necessary in a medical emergency. In this case, the use of the concomitant medication will be reported as soon as is practical.

6.2. Diet, Fluid, and Activity Control

Subjects are required to refrain from use of tobacco, smoking cessation products, and nicotine-containing products within 3 months prior to Screening through EOT or ET.

Consumption of foods or beverages containing grapefruit/grapefruit juice or Seville oranges or its juice within 7 days prior to Check-in (Day -1) and through EOT or ET will not be allowed unless deemed acceptable by the Investigator (or designee) and Sponsor.

Consumption of alcohol- or caffeine-containing foods or beverages within 72 hours prior to Check-in (Day -1) and through EOT or ET will not be allowed unless deemed acceptable by the Investigator (or designee) and Sponsor.

Subjects will refrain from strenuous exercise from 5 days prior to Check-in (Day -1) and during the period of confinement at the CRU and will otherwise maintain their normal level of physical activity through EOT or ET (ie, should not begin a new exercise program or participate in any unusually strenuous physical exertion).

While confined at the CRU, subjects will receive a standard diet at scheduled times that do not conflict with other study-related activities.

Fasting requirement in relation to dosing are described in [Section 3.1](#) and [Section 5.2](#).

7. STUDY ASSESSMENTS AND PROCEDURES

7.1. Pharmacokinetic Assessments

7.1.1. Pharmacokinetic Blood Sample Collection and Processing

Blood samples for PK analysis of LOXO-305 plasma levels will be collected at the timepoints specified in [Appendix 4](#). The exact time of the study drug administration and the actual time of blood sampling for PK analysis will be recorded on the eCRF.

Processing, storage, and shipping instructions for these PK blood samples will be provided in a separate Laboratory Manual. The number of blood samples and total blood volume required for PK testing is presented in [Appendix 3](#).

7.1.2. Analytical Methodology

Concentrations of LOXO-305 in plasma will be determined using a validated bioanalytical method. Specifics of the bioanalytical methods will be provided in a separate document.

7.2. Safety and Tolerability Assessments

Safety evaluations may be repeated at the discretion of the Investigator (or designee) or Sponsor.

Every effort will be made to schedule and perform the procedures in accordance with the nominal time, giving considerations to appropriate posture conditions, practical restrictions, and any other procedures to be performed at the same timepoint. The order of priority for scheduling procedures around a timepoint is (in descending order of priority):

- dosing
- PK blood sampling
- 12-lead ECGs
- vital sign measurements
- blood and urine samples for clinical laboratory evaluations
- physical examination.

7.2.1. Adverse Events

Adverse event definitions; assignment of severity, causality, action taken, and outcome; and procedures for reporting SAEs are detailed in [Appendix 1](#).

Subjects will be asked a non-leading HDYF? question such as “Have there been any changes in your health status since Screening/since you were last asked?” at the timepoints specified in [Appendix 4](#) (ie, at Screening [after the ICF is signed], at Check-in [Day -1], at each postdose vital sign measurement, and at an appropriate time for all other days). Subjects will also be encouraged to voluntarily report AEs occurring at any other time through the EOS.

Adverse events, whether volunteered, identified by the subject's responses to HDYF? inquiries, or noted on physical examination, ECG, vital sign measurements, or clinical laboratory evaluations, will be recorded throughout the study (ie, from signing of the ICF until EOS [or ET if the subject discontinues from the study and does not complete a follow-up phone call]), either as subject medical history (if the event is reported as beginning prior to signing of the ICF or if the event occurs prior to study drug administration on Day 1 and is assessed as not related to study procedures by the Investigator [or designee]) or as AEs (if the event occurs after signing of the ICF but prior to study drug administration on Day 1 and is assessed as related to study procedures by the Investigator [or designee], or if the event occurs after study drug administration on Day 1 through EOT or ET regardless of relationship to study drug). From EOT or ET through EOS, only AEs assessed as related to study drug by the Investigator (or designee) are to be reported. All SAEs that develop from the time of ICF signing until EOS (or ET, if the subject discontinues from the study and does not complete a follow-up phone call) are to be reported.

Unless a subject withdraws consent or is withdrawn from the study and does not complete the follow-up phone call, all subjects must be followed until EOS. Subjects with AEs that are assessed as related to study drug by the Investigator (or designee) which are ongoing at EOS may continue to be followed until the symptoms or value(s) return to normal, or acceptable levels, as judged by the Investigator (or designee) and confirmed by the Sponsor. The Investigator (or designee) should use appropriate judgment in ordering additional tests as necessary to monitor the resolution of events. The Sponsor may request that additional safety tests be performed.

Subjects will receive a follow-up phone call 7 days (\pm 2 days) after EOT or ET to determine if any SAE or drug-related AE has occurred since the EOT or ET visit.

At all times, a subject may be required to remain at the CRU for longer at the discretion of the Investigator (or designee).

Any event that meets the criteria of a suspected unexpected serious adverse reaction (SUSAR) will be reported to the Institutional Review Board (IRB) according to CRU policy by the Investigator (or designee) and to regulatory authorities by the Sponsor (or Sponsor designee) according to regulatory authority requirements. Refer to Reference Safety Information in the current IB¹ for LOXO-305 for expected adverse reactions.

7.2.2. Clinical Laboratory Evaluations

Clinical laboratory evaluations (clinical chemistry panel [fasted at least 8 hours; at EOT or ET, subjects are not required to be fasted prior to clinical laboratory evaluations], coagulation parameters, hematology panel, TSH [Screening only], HbA1c [Screening only], estimated glomerular filtration rate [Screening and Check-in/Day -1], and UA) will be collected at the timepoints specified in [Appendix 4](#).

Screens for HCV antibody, HBV core antibody, HBsAg, and HIV antibody will be performed at Screening.

Testing for COVID-19 via PCR (or equivalent) will be performed at the timepoints specified in [Appendix 4](#). Testing for COVID-19 may also be conducted periodically during the subject's CRU confinement, at the discretion of the Investigator (or designee). Further details

regarding COVID-19 testing (including procedures who test positive at any time throughout CRU confinement) are specified in separate documents.

A urine drug screen for selected drugs of abuse (including cotinine and alcohol) will be performed at Screening and repeated at Check-in (Day -1) for all subjects.

A serum qualitative pregnancy test (female subjects only [serum quantitative may be used for confirmation if needed]) and an FSH test (post-menopausal female subjects only) will be performed at the timepoints specified in [Appendix 4](#).

The number of blood samples and total blood volume required for clinical laboratory evaluations are presented in [Appendix 3](#). A list of the specific evaluations is in [Appendix 2](#).

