4.2. Check-in Procedures (Day -1)

At Check-in (Day -1), subjects will report to the CRU and the following procedures will be performed:

1. Review of inclusion/exclusion criteria
2. Interim medical history, including concomitant medication(s)
3. Weight and BMI
4. Complete physical examination ([Section 7.2.5](#))
5. 12-lead ECG measured after the subject has been resting in the supine position for at least 10 minutes ([Section 7.2.4](#))
6. Vital sign measurements (including oxygen saturation, oral temperature, respiratory rate, and supine BP and pulse rate [measured after the subject has been supine for at least 5 minutes]; [Section 7.2.3](#))
7. HDYF? inquiry, AE, SAE, and concomitant medication evaluations ([Section 7.2.1](#))
8. Clinical laboratory evaluations ([Section 7.2.2](#); clinical chemistry panel [fasted at least 8 hours], coagulation parameters, hematology panel, and UA; [Appendix 2](#))
9. Screen for COVID-19 via PCR or equivalent
10. Screen for selected drugs of abuse, including cotinine and alcohol ([Appendix 2](#))
11. Estimated glomerular filtration rate ([Appendix 2](#))
12. Serum pregnancy test (for female subjects only; [Appendix 2](#))
13. Compliance with concomitant medications and exclusionary restrictions ([Section 6](#))

For subjects to continue their participation in the study, the inclusion/exclusion criteria must continue to be met at Check-in (Day -1 [as appropriate; #1, [Section 4.2](#)]). In addition, continued compliance with concomitant medication and other restrictions will be verified.

The Sponsor will review medical history and all screening evaluations for potential subjects prior to enrollment. Prior to dosing, the Sponsor will provide approval of subjects selected for enrollment by the Investigator (or designee).

Subjects who meet all the inclusion criteria and for whom none of the exclusion criteria apply will be eligible to be enrolled into the study. Safety evaluations may be repeated at the discretion of the Investigator (or designee) or Sponsor.

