Appendix 2: Clinical Laboratory Evaluations

Clinical Chemistry Panel (Fasted):	Hematology Panel:	Other Tests:
Alanine aminotransferase (ALT) Albumin Alkaline phosphatase (ALP) Amylase Aspartate aminotransferase (AST) Bilirubin (direct and total) Blood urea nitrogen Calcium Chloride Cholesterol Creatine kinase Creatinine Glucose Iron Lipase Magnesium Phosphorus Potassium Sodium Total protein Triglycerides Uric acid	Hematocrit Hemoglobin Mean corpuscular hemoglobin Mean corpuscular hemoglobin concentration Mean corpuscular volume Platelet count Red blood cell (RBC) count RBC distribution width White blood cell (WBC) count WBC differential (percent and absolute): Basophils Eosinophils Lymphocytes Monocytes Neutrophils	Hemoglobin A1c (HbA1c) ^b Thyroid-stimulating hormone (TSH) ^b Estimated glomerular filtration rate ^a SARS-CoV-2 (COVID-19) Testing
		Coagulation Parameters: Partial thromboplastin time Prothrombin time International normalized ratio
		Serology: Human immunodeficiency virus (HIV) antibody Hepatitis B surface antigen (HBsAg) Hepatitis B virus (HBV) core antibody Hepatitis C virus (HCV) antibody
		For Female Subjects only: Pregnancy test (serum qualitative, serum quantitative may be used for confirmation if needed) ^c Follicle-stimulating hormone (post-menopausal female subjects only) ^b
Urine Drug Screen: ^a	Bilirubin Color and appearance Glucose Ketones Leukocyte esterase Nitrite Occult blood pH and specific gravity Protein Urobilinogen Microscopic examination including bacteria, casts, crystals, epithelial cells, RBCs, and WBCs (if protein, leukocyte esterase, nitrite, or blood is positive)	

a. Performed at Screening and Check-in (Day -1) only.

- a. Performed at Screening and
- b. Performed at Screening only.

c. Performed at Screening, Check-in (Day -1), and End of Treatment (EOT) or Early Termination (ET) only.

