Appendix 4: Schedule of Assessments

Study Procedures ^a	Screening (Days -29 to -2)	Check-in (Day -1)	Study Conduct							Clinic Discharge/ EOT/ET ^t	Follow-up Phone Call (EOS)
			1	2	3	4	5	6	7		
Confined to the CRU		X	X	X	X	X	X	X	X	X	
Inclusion/Exclusion Criteria	X	X									
Informed Consent	X										
Demographics	X										
Medical History	X	X ^b									
Height/Weight/BMI	X ^c	X ^c									
Physical Examination ^d		X								X	
12-lead ECG ^e	X	X	X	X		X				X	
Vital Signs ^f	X ^{g,h}	X ^{g,h}	X ^h	X	X	X	X	X	X	X ^{g,h}	
HDYF? Inquiry ⁱ	X	X	X	X	X	X	X	X	X	X	X
AEs/SAEs ^j	X	X	X	X	X	X	X	X	X	X	X
LOXO-305 Administration			X ^k								
CCI											
Clinical Laboratory Evaluations ⁿ	X	X				X				X ^u	X ^u
Estimated Glomerular Filtration Rate	X	X									
Hepatitis and HIV Screen	X										
COVID-19 Testing ^o	X	X									
HbA1c Test	X										
Drug Screen ^p	X	X									
Prior and Concomitant Medications ^q	X	X	X	X	X	X	X	X	X	X	X
Serum Pregnancy Test ^r	X	X								X ^u	X ^u
FSH Test ^s	X										
TSH Test	X										

Abbreviations: AE = adverse event; BMI = body mass index; BP = blood pressure; COVID-19 = SARs Coronavirus 19; CRU = Clinical Research Unit; ECG = electrocardiogram; EOS = End of Study; EOT = End of Treatment; ET = Early Termination; FSH = follicle-stimulating hormone; HbA1c = hemoglobin A1c; HDYF? = How Do You Feel?; HIV = human immunodeficiency virus; ICF = Informed Consent Form; PK = pharmacokinetic; SAE = serious adverse event; TSH = thyroid-stimulating hormone; UA = urinalysis.

- a. For details on study procedures, see [Section 7](#).
- b. Interim medical history only.
- c. Height collected at Screening only, body mass index based on Screening height.
- d. A complete physical examination will be performed at Check-in (Day -1). An abbreviated physical examination will be performed on Day 8 (End of Treatment [EOT]) or Early Termination (ET).
- e. 12-lead electrocardiograms (ECGs) will be obtained prior to and as close as possible to the scheduled blood draws at Screening and Check-in (Day -1), and at the following times related to administration of each Treatment: Day 1 (predose and 2 and 4 hours after LOXO-305 dosing), Day 2, Day 4, and Day 8 (EOT) or ET. 12-lead ECGs will be collected after the subject has rested in the supine position for at least 10 minutes.

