- n. Clinical chemistry panel (fasted for at least 8 hours), coagulation parameters, hematology panel, and urinalysis (UA) will be performed.
- o. Testing for COVID-19 will be conducted at a minimum at Screening and Check-in (Day -1). Testing for COVID-19 may also be conducted periodically during the subject's CRU confinement, at the discretion of the Investigator (or designee). Tests will be performed by rapid polymerase chain reaction or equivalent.
- p. Drugs of abuse urine test, including cotinine and alcohol. Results from the drugs of abuse tests will be used to determine subject eligibility per the inclusion/exclusion criteria.
- q. Prior and concomitant medication administration will be recorded beginning at informed consent. In addition, all Investigator-approved medications taken by a subject within 14 days prior to study drug administration (Day 1) for prescription medications and non-prescription medication, will be recorded on the subject's electronic Case Report Form.
- r. Female subjects only.
- s. Post-menopausal female subjects only.
- t. EOT is defined as when the subject is released from the CRU following completion of all assessments through Day 8. ET is defined as when the subject is released from the CRU if the subject terminates the study early. Vital sign measurements, ECG, and abbreviated physical examination results are to be available for review by the Investigator (or designee) prior to subject release from the CRU at the EOT visit. Clinical laboratory evaluations for clinical chemistry, hematology, coagulation, and UA and pregnancy test results (female subjects only) are to be available for review by the Investigator (or designee) prior to subject release from the CRU at the EOT visit and prior to subject release from the CRU at the ET visit, if available.
- u. Clinical laboratory evaluations and pregnancy test (female subjects only) will be performed on the day prior to subject release from the CRU (Day 7) if the subject completes the study (EOT). Clinical laboratory evaluations and pregnancy test (female subjects only) will be performed on the day of subject release from the CRU if the subject terminates early (ET).

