8.1.3. Definitions of Baseline and Change from Baseline

Baseline value is defined as the last non-missing measurement before administration of LOXO-305.

If the date/time of the value is incomplete or missing, it will be excluded from the baseline calculation, unless the incomplete date/time indicates the value was recorded prior to dosing.

Individual changes from baseline will be calculated by subtracting the individual subject's baseline value from the value at the timepoint. The mean change from baseline will be defined as the mean of the individual changes from baseline for all subjects.

See [Section 8.1.2](#) for more detail on handling repeat and unscheduled readings in the calculations.

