8.6.2. Clinical Laboratory Parameters

All clinical laboratory evaluations, with changes from baseline, will be listed; any value outside the clinical reference range will be flagged, and whether the out of range value was deemed clinically significant or not clinically significant will be indicated. Separate listings will be provided for any parameter for which there is any individual subject value outside the respective clinical reference range.

The observed results and change from baseline for clinical chemistry, hematology, and coagulation parameters will be summarized descriptively by treatment and timepoint.

Values recorded as $< x$, $\leq x$, $> x$, or $\geq x$ will be displayed in the listings as recorded. For the derivation of listing flags, calculation of summary statistics, and presentation in the figures, $< x$ and $\leq x$ values will be set to 0, whereas $> x$ and $\geq x$ values will be set to x .

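### Protocol 7.2.2 waives fasting for end-of-treatment chemistry, the appendices do not, and the EOT change from a fasted baseline may therefore carry a meal effect that cannot be identified afterwards

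*Protocol*

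**What the plan says.** Three places in the protocol set the fasting state of the chemistry sample, and they do not agree.

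- Section 7.2.2 gives the general 8-hour rule and then an exemption: "at EOT or ET, subjects are not required to be fasted prior to clinical laboratory evaluations".
- Appendix 4, footnote n, covers the whole laboratory row of the schedule and has no exemption: "Clinical chemistry panel (fasted for at least 8 hours), coagulation parameters, hematology panel, and urinalysis (UA) will be performed".
- Appendix 2 heads the panel "Clinical Chemistry Panel (Fasted"), again with no exemption.

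The Check-in list in Section 4.2 asks for "clinical chemistry panel [fasted at least 8 hours], coagulation parameters, hematology panel, and UA". In the schedule, the laboratory row has two postdose entries: Day 4 and EOT/ET. Footnote u says the EOT laboratory work "will be performed on the day prior to subject release from the CRU (Day 7) if the subject completes the study (EOT"); for early terminators it is done on the day of release.

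In the SAP, Section 8.1.3 states: "Baseline value is defined as the last non-missing measurement before administration of LOXO-305". Section 8.6.2 states: "The observed results and change from baseline for clinical chemistry, hematology, and coagulation parameters will be summarized descriptively by treatment and timepoint". It also has out-of-range values flagged, marked for clinical significance and, by parameter, listed separately. Section 8.1.2 leaves postdose repeats and unscheduled values out of every calculation, and Section 8.1.1 leaves ET data out of the summary statistics.

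**The concern.** A change from baseline reflects the drug only if the two samples were taken under like conditions or a control group shares the difference. Here a stated rule allows the conditions to differ at one of two scheduled postdose chemistry timepoints, and every subject receives LOXO-305. If subjects eat before the Day 7 draw, a rise in glucose or triglycerides enters the EOT table, and possibly the out-of-range listing, looking like any other postdose change. EOT is also where a reader looks to see whether a Day 4 change has resolved, and a fed sample can imitate persistence.

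Safety and tolerability are the primary objective, so the comparability of the laboratory data deserves care even though nothing is tested. The contradiction is also an operational problem: staff working from Section 7.2.2 and staff working from Appendix 4 could draw different samples, and practice could differ between cohorts.

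**Working it through.** The plan states no figure on this point, so there is none to reproduce. The check sets the texts side by side and then illustrates sensitivity.

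**1. Fasting state by timepoint**

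| Chemistry sample | Fasting state | Source | Role in the SAP summary |
|---|---|---|---|
| Check-in (Day -1) | Fasted, at least 8 h | Protocol 4.2, 7.2.2 | Normally the baseline, as no laboratory draw is scheduled on Day 1 |
| Day 4 | Fasted, at least 8 h | Protocol 7.2.2, Appendix 4 note n | Postdose change |
| EOT (drawn Day 7) | Waived in 7.2.2; fasted in Appendix 2 and Appendix 4 note n | As listed | Postdose change |
| ET | Same conflict | As listed | Not summarised (SAP 8.1.1) |

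Only the completers' Day 7 sample is both summarised and of uncertain fasting state. The 8-hour rule attaches to the chemistry panel, so hematology and coagulation are not affected.

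**2. Could a meal effect be identified later?** Neither document requires fasting status to be recorded at a draw (the case report form itself is not among the documents). There is no control group. A fasted repeat would count as unscheduled under SAP 8.1.2 and be excluded, while the original value stays in.

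**3. How a meal shift passes into the mean.** Let f be the fraction of the cohort that is fed and m the mean rise due to the meal. The spurious mean change is f × m. It does not shrink as the cohort grows. With all subjects fed it is m; with half fed it is 0.5m.

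**4. Sensitivity, under assumed values.** The documents give no m, so it is expressed in standard deviations (SD) of the individual changes, over an assumed range of 0.5 to 2. Inputs: n = 6 per cohort (Protocol 8.1), all six fed, no drug effect.

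- Half-width of a 95% interval for the mean change: t(0.975, 5 df)/√6 = 2.571/2.449 = 1.05 SD.
- Probability that this interval excludes zero, from the noncentral t distribution with noncentrality m√6: 0.17 for m = 0.5, 0.51 for m = 1 and 0.97 for m = 2, against 0.05 with no shift.

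The SAP plans no such interval or test. The figures show only how easily a shared shift could look like a signal in six subjects.

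**5. What Day 4 still offers.** Protocol 1.3.2 gives a half-life of about 20 h, and Section 3.1 implies about 24 h (72 h taken as roughly 3 half-lives). The residual fraction is 0.5^(t/half-life):

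- Day 4 (72 h): 0.5^(72/20) = 8.25% and 0.5^(72/24) = 12.5%.
- Day 7 (144 h): 0.5^(144/20) = 0.68% and 0.5^(144/24) = 1.56%.

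The clean, fasted comparison is therefore the one taken at higher residual drug.

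**The case against.** The strongest reply is that the waiver is deliberate and permissive. Section 7.2.2 names EOT and ET explicitly, and Appendix 4 footnote a sends the reader to Section 7 for procedural detail. On that view the appendices are shorthand and 7.2.2 governs. This is a fair account of which text prevails, but it does not help the comparison: if 7.2.2 governs, a fed EOT sample is allowed.

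A reader might go further and infer that EOT samples are fed, so that the EOT change is confounded as a matter of fact. The documents do not support that. They lift a requirement and do not prescribe a meal. They give no clock time for the Day 7 draw and no meal times. If blood is taken before breakfast, nothing is mixed.

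A reader might also infer that meal effects would distort dose escalation. Laboratory data are part of the review in Protocol 5.5, but the listed triggers are drug-related grade 3 or higher toxicities judged clinically significant, and observed or predicted C_max. Mean chemistry change is not among them, and nothing shows that a meal effect would reach a trigger.

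Other mitigating points also stand. The safety analysis is descriptive (SAP 8.6.6), out-of-range values are marked for clinical significance, safety evaluations may be repeated (Protocol 7.2), and Day 4 is a fasted comparison. The clinical-significance mark does not correct the summary table, and a repeat does not enter it.

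**Conclusion.** The concern holds in a limited form. The fasting statements in Section 7.2.2, Appendix 2 and Appendix 4 contradict one another. Under 7.2.2 the EOT change from baseline may mix meal and drug effects for meal-sensitive analytes, with no means in the plan of separating them afterwards.

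The size is unknown. The documents give no meal effect, and the sensitivity figures rest on an assumed shift of 0.5 to 2 SD with all six subjects fed. The effect is zero if all subjects happen to be fasted. The consequence is confined to EOT chemistry summaries and out-of-range flags. Day 4 chemistry, hematology, coagulation and the listed escalation triggers are not shown to be affected. It is worth correcting because it touches one of two scheduled postdose chemistry timepoints for the primary objective and the remedy is small.

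**What to change.** Make the three protocol passages agree by limiting the waiver in Section 7.2.2 to ET. Completers' Day 7 chemistry would then be drawn after at least 8 hours' fast, as at Check-in and Day 4. Carry the ET exception into Appendix 2 and Appendix 4 footnote n so that all three read alike.

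Record fasting status at each chemistry draw, and add to SAP 8.6.2 that any non-fasted EOT or ET value is flagged in the listings. If the sponsor prefers to keep the EOT waiver, the recording and flagging are the minimum: they would not remove a meal effect from the summary but would let a reader see where one is possible.

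The cost is a wording change, scheduling the Day 7 draw before a meal for subjects who are already confined, and one extra data field. ET draws, which may be unplanned, keep their exemption, and the summaries lose nothing because ET values are already excluded.
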